**International multicenter double-blind placebo-controlled
randomized parallel group clinical trial of efficacy of
Anaferon for children in the treatment of influenza and
acute respiratory viral infections in children**

Phase IV

Sponsor	OOO «NPF «MATERIA MEDICA HOLDING»
Protocol number	MMH-AD-004
Version date:	August 01, 2016
ClinicalTrials.gov Id:	NCT02072174

Protocol Summary

This document represents the protocol summary for the study on human subjects. The study will be carried out in accordance with ICH GCP, National Standard of the Russian Federation GOST 52379-2005 "Good Clinical Practice", Helsinki Declaration of World Medical Association, relevant requirements of the regulatory authorities as well as the study procedures.

Title of Study

International multicenter double-blind placebo-controlled randomized parallel group clinical trial of efficacy of Anaferon for children in the treatment of influenza and acute respiratory viral infections in children.

Phase: IV

Sponsor: OOO "NPF "Materia Medica Holding", Moscow, Russia

Protocol No. MMH-AD-004

Study purposes

- To obtain additional data on therapeutic efficacy of Anaferon for children in the treatment of influenza and acute respiratory viral infections (ARVI) in children.

Endpoints

Primary endpoint

1. Average illness duration (until recovery¹ or significant improvement²).

Secondary endpoints

1. Percentage of patients with recovery¹/improvement² in health on days 2, 3, 4 and 5 of observation treatment (according to the patient's diary), on days 3 and 5 of therapy (according to physician's objective examination).
2. Changes in fever (changes in temperature on days 2, 3, 4 and 5 of observation treatment).
3. Percentage of patients with normal body temperature ($\leq 37.0^{\circ}\text{C}$) on days 2, 3, 4 or 5 of observation treatment.
4. Severity of clinical manifestations of influenza/ARVI in scores on days 3 and 5 of observation treatment – according to physician's objective examination; on days 2-6 of observation – according to patient's diary.
5. Assessment of the Severity of Influenza Virus / ARVI Using the "Area Under the Curve" for an Overall Symptom Assessment (based on the results of area under curve for total

¹ **Recovery criteria:** temperature $\leq 37.0^{\circ}\text{C}$ + lack of symptoms within 24 hours.

² **Improvement criteria:** temperature $\leq 37.2^{\circ}\text{C}$ + total symptom score ≤ 2 .

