⁴ Viral load will be evaluated in subjects with positive rapid test for influenza A and B. Viral RNA levels [influenza A/B] \log_{10} copies/mL in nasal and oral swabs will be determined by real-time RT-PCR.

thermometer Geratherm Classic) as well as intensity of the disease symptoms. Training on the diary filling will be performed for parents/adoptive parents.

The subject will be followed for 14 days (screening, randomization – 1 day, treatment – 5 days, follow-up – 1 day; delayed phone “visit” – day 14).

During the treatment and follow-up periods the subject/physician shall make 4 visits, the fifth phone “visit” is stipulated additionally: 1) physician/subject visits – on days 1, 3, 5 and 7 (Visits 1, 2, 3 and 4) – at medical facility or at home; 2) phone “visit” (Visit 5) – on day 14.

At visits 2-4 the physician shall record objective examination findings, collect nasopharyngeal swabs for further PCR diagnosis in subjects with positive rapid test (to determine viral load and its reduction against therapy), monitor the prescribed and concomitant therapy, revise the patient’s diary. Phone “visit” will be made to inquire on the subject’s condition, presence/absence of secondary bacterial/viral complications, administration of antibacterial drugs.

Symptomatic therapy and therapy of co-morbidities is allowed except for the products specified in section “Prohibited concomitant therapy”.

Inclusion and exclusion criteria

Inclusion criteria

1. Subjects of both sexes aged 3-12 years inclusively.
2. Diagnosis of influenza/ARVI according to physician’s examination: body temperature $\geq 38.0^{\circ}\text{C}$ at the time of examination + symptom score ≥ 4 (at least 1 systemic symptom ≥ 2 and 1 nasal/throat/chest symptom ≥ 2 or several symptoms ≥ 1 score).
3. The first 24 hours from the beginning of manifestations of influenza/ARVI.
4. The possibility to start therapy within 24 hours from the first symptoms of ARVI.
5. Availability of patient information sheet (informed consent form) for parents/adoptive parents for participation in the study signed by one of the parents/adoptive parents.

Exclusion criteria

1. Suspected pneumonia, bacterial infection or severe disease requiring antibacterial products (including sulfanilamides) starting from the first day of the disease.
2. Clinical symptoms of severe influenza/ARVI⁵ requiring hospitalization.

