Study design scheme

Schedule of study procedures

Procedure/Visit	Visit 1 (Day 1)	Visit 2 (Day 3)	Visit 3 (Day 5)	Visit 4 (Day 7)	Visit 5 (Day 14±1)
Obtaining signed informed consent form (ICF)	+				
Collection of complaints	+	+	+	+	
Collection of medical history	+				
Objective examination	+	+	+	+	
Recording influenza/ARVI symptoms	+	+	+	+	
Inclusion/exclusion criteria assessment	+				
Recording concomitant therapy	+	+	+	+	
Rapid test for influenza viruses in nasal swabs	+				
Obtaining nasal and oropharyngeal	+	+	+	+	

swabs for PCR diagnosis of influenza (in case of positive result of rapid test for influenza)					
Obtaining nasal and oropharyngeal swabs for PCR diagnosis of other respiratory viruses (in case of negative result of rapid test for influenza)	+				
Randomization and prescription of the study therapy	+				
Issue of the study product	+				
Issue of antipyretic product	+				
Accounting and return of the study product, determination of compliance				+	
Issue of patient's diary	+				
Revision of correctness of diary filling		+	+	+	
Diary return				+	
Therapy safety assessment		+	+	+	+
Phone contact					+

Statistical Analyses

Samples

Statistical analysis will be carried out in the following sets:

Total set – all enrolled subjects whose parents/adoptive parents had signed ICF. This set will take into account all adverse events and related conditions during the study including prior to the study therapy initiation.

Total set of the subjects receiving at least one dose of the study product will be used for safety and tolerability analysis (Safety population), as all adverse events recorded in the subject after administration of the product will be taken into account.

Full Analysis Set. This set includes all enrolled subjects excluding those having at least one of the following events:

- 1) non-compliance with inclusion/exclusion criteria;
- 2) the subject did not receive a single dose of the study product;
- 3) lack of any data on the subject after prescription of the study product

This set most fully conforming to Intention-to-treat principle will be used for Intention-to-treat analysis (ITT-analysis) of the study product efficacy.

Per Protocol set. This set includes all subjects receiving per protocol therapy in full, completing all scheduled visits and having no major deviations from the protocol. This set will be used for Per Protocol analysis (PP-analysis) of the study therapy efficacy.

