Last Observation Carried Forward (LOCF) will be used for filling missing values.

Evaluation of sample size

Evaluation of sample size was based on the following rules and assumptions:

1. Statistical provisions.
 - 1.1 Power of statistical criteria " $P = (1 - \beta)$ " is considered to be equal to 80% (probability of correct rejection of null hypothesis is 0.8).
 - 1.2 Probability of error of the first kind " α " is admitted to be $< 5\%$ (probability of erroneous acceptance of alternative hypothesis is < 0.05).
 - 1.3 The statistical criteria used are two-sided.
 - 1.4 Calculation of total sample size was based on the assumptions on expected effects on primary endpoint claimed in the protocol.
 - 1.5 Effect of interim statistical analyses on probability of error of the first kind is regulated at each point (interim analysis, final analysis) using O'Brien-Fleming boundary.

2. Assumptions on expected clinical study effects.

It is assumed that the difference between average disease duration (until recovery or significant improvement) in Anaferon for children and Placebo groups will be less than 0.5 days, while standard deviation in both groups will not exceed 2 days.

Taking into account that statistical analysis will be performed twice – at interim analysis and at final analysis – based on the assumed effect the minimum required size of each group (product and placebo) will be as follows:

Number of subjects	Interim analysis	Final analysis
Number of subjects in both groups	254	508
including		
- number of subjects in Anaferon group	127	254
- number of subjects in Placebo group	127	254

Given withdrawal at screening, including due to negative rapid influenza test (the ratio is 1 subject with positive test/5-6 subjects with influenza-like symptoms and negative influenza test) and during the study, the final sample size will be 972 subjects to be enrolled.

This calculation is made using the formula: $N_T = N_{PP} / (1 - C_w)$, where N_T – final sample size; N_{PP} – scheduled number of subjects completing the study per protocol ($N_{PP}=508$); C_w – withdrawal coefficient ($C_w=0.4774$).

Interim analysis

Interim analysis of *Particular Per Protocol (pPP)* is scheduled within the study.

Purposes of interim analysis:

- Ability to adjust sample size in case in minor deviation of the effect achieved from the effect specified at baseline;

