- Ability of early discontinuation of the study in case of major deviation⁷ of the effect achieved from the effect specified at baseline.

Within the protocol one interim analysis point has been scheduled.

Interim analysis is scheduled for the time when at least 127 subjects in each group complete the study, i.e. receive per protocol therapy in full, undergo all scheduled visits and have no major protocol deviations.

Statistical criteria

All statistical calculations will be made using the following groups of statistical criteria:

- parametric – to assess continuous and interval accidental values;
- non-parametric – to obtain:

⁷ Early study termination is possible both on safety reasons in case of lack of efficacy and after the required power of statistical efficacy conclusions is achieved.

- evaluations on equality/inequality of proportions of subjects compared for various visits,
 - analysis of frequencies in features compared,
- and
- evaluation of continuous and interval accidental values in case of violation of requirement on normal sample distribution;
 - interim analysis procedures.

Parametric criteria will be checked for normalcy of the samples compared (Kolmogorov-Smirnov test).

The following *parametric methods and approaches* are suggested:

1. To evaluate various continuous variables obtained in two different (independent) groups – Student’s test for independent samples.
2. To evaluate differences in continuous variables obtained in one group at two different visits – Student’s test for paired samples.
3. For multiple assessment at different visits – Bonferroni’s test (Student’s test modification for multiple comparisons).
4. For comparison of several sample means with baseline (control) – Dunnett’s test (Student’s test modification for multiple comparisons with control).
5. For evaluation of time changes in parameters under comparison – analysis of variance (ANOVA, MANOVA) in modification with repeated measures.

To carry out the statistical analysis and approaches specified above the following SAS procedures are suggested:

- UNIVARIATE – check for normalcy of distributions compared;
- CORR, MEANS – calculation of descriptive statistics;
- TTEST – Student’s test with all modifications;
- GLM, GENMOD, GLIMMIX – analysis of variance (ANOVA/ANCOVA, MANOVA/MANCOVA).

Nonparametric criteria:

1. For evaluation of differences in continuous variables obtained in two various (independent) groups – Mann-Whitney test;

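### No covariate-adjusted primary analysis is prespecified: the only two-group tests listed for a continuous outcome are unadjusted, which forgoes some efficiency

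*Combined protocol and SAP*

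**What the plan says.** The primary endpoint is "Average illness duration", measured to recovery or significant improvement (Endpoints). No test is tied to it by name.

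The Statistical criteria section gives a menu of suggested methods:

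- Parametric item 1, "To evaluate various continuous variables obtained in two different (independent) groups": Student's test for independent samples.
- Nonparametric item 1, "For evaluation of differences in continuous variables obtained in two various (independent) groups": Mann-Whitney, for use when the normality check fails.
- SAS procedures: GLM, GENMOD and GLIMMIX are labelled "analysis of variance (ANOVA/ANCOVA, MANOVA/MANCOVA". The list serves the methods above it, and the only analysis of variance among those is the repeated-measures one for changes over time.

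No covariate, stratification factor or adjusted model is named for any efficacy endpoint.

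Candidate covariates are nevertheless available at Visit 1. Inclusion criterion 2 requires temperature "at the time of examination + symptom score" to reach set thresholds, so both are measured before treatment. Age is known from inclusion criterion 1 and country from enrolment (Number of subjects: 772, 100 and 100). The Schedule of study procedures also places "Rapid test for influenza viruses in nasal swabs" at Visit 1.

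**The concern.** How ill a child is at entry, the child's age and the country of care may plausibly predict how long the illness lasts. Where they do, an unadjusted comparison leaves their contribution in the error term and leaves any chance imbalance between arms uncorrected. Adjustment removes both without recruiting another child.

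The listed methods contain no adjusted two-group comparison, and the sample size assumes no reduction in variance. A covariate model also has to be fixed in advance. If it is not, adjustment will either be left out or be chosen once the data are known.

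**Working it through.** **Inputs from the documents** (Evaluation of sample size): difference 0.5 day; "standard deviation in both groups will not exceed 2 days", taken as SD = 2; power 80%; two-sided tests; "probability of erroneous acceptance of alternative hypothesis is < 0.05", taken as alpha 0.05; one interim at 127 of 254 per arm, that is, half the information; O'Brien-Fleming boundary. The text words the difference as less than 0.5 day, but 0.5 is the value that reproduces the sample size.

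**Input assumed:** R², the share of variance in illness duration explained by baseline covariates. The documents give no value, so the range runs from 0 to 0.30.

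**Step 1: reproduce the plan's figure.**

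- Fixed design: n per arm = 2 × SD² × (1.960 + 0.842)² / 0.5² = 2 × 4 × 7.849 / 0.25 = 251.2.
- The two-look O'Brien-Fleming bounds at half information are 1.977 × √2 = 2.797 at the interim and 1.977 at the end. The inflation factor is 1.0078.
- 251.16 × 1.0078 = 253.1, rounded up to **254 per arm**. This matches the plan.
- Enrolment: 508 / (1 − 0.4774) = 972.06, against 972 in the plan.

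The planned size is therefore exactly that of an unadjusted comparison of means. Its power over both looks at 254 per arm is 80.1%.

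**Step 2: put in the adjustment.** Residual SD = 2 × √(1 − R²). The expected final test statistic is 0.5 / (residual SD × √(2/254)). Power is the probability of crossing either bound, from the bivariate normal distribution with correlation √0.5. The unadjusted trial of equal precision has 254 / (1 − R²) per arm.

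| R² (assumed) | Residual SD | Expected final Z | Power at 254 per arm | Equivalent unadjusted n per arm |
|---|---|---|---|---|
| 0 | 2.000 | 2.82 | 80.1% | 254 |
| 0.01 | 1.990 | 2.83 | 80.5% | 257 |
| 0.02 | 1.980 | 2.85 | 80.9% | 259 |
| 0.05 | 1.949 | 2.89 | 82.1% | 267 |
| 0.10 | 1.897 | 2.97 | 84.1% | 282 |
| 0.20 | 1.789 | 3.15 | 88.1% | 318 |
| 0.30 | 1.673 | 3.37 | 91.9% | 363 |

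**Step 3: the downside.** Symptom score, temperature, age and two country terms use five degrees of freedom. If all five explained nothing, the variance of the adjusted difference would rise by about 5/500 = 1%, where 500 = 508 − 2 − 5 − 1. Power would then be about 79.7%, a loss of under half a point.

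These figures apply to a comparison of means. They do not carry over to Mann-Whitney or to a time-to-event model.

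**The case against.** **The test is not assigned.** A reader might infer that the plan declares an unadjusted Student's test as its primary analysis. It does not. That test stands in a generic list of suggestions, and the same section lists procedures that can fit ANCOVA. The document also calls itself a protocol summary. This stands: the accurate statement is that no adjusted primary model is specified and that the two-group tests listed are unadjusted.

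**The gain may be small.** Entry requires temperature of at least 38.0°C, a symptom score of at least 4 and onset within 24 hours. This narrows the spread of two proposed covariates. About 79% of planned enrolment (772 of 972) is in one country. At R² of 1% or 2% the gain is under one point. This stands too. However, the thresholds cut from below only, they do not restrict age or country, and Step 3 shows that the loss is slight if the covariates turn out useless.

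**Power is already adequate.** A reader might infer that the trial is underpowered without adjustment. The documents do not support that: 80% is the stated target and 254 per arm meets it. The SD of 2 is also given as a ceiling; at SD 1.9 the unadjusted power would be 84.0%, and at 1.8 it would be 87.7%.

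**The rapid-test result may not vary.** It is tempting to add it as a covariate for every child. Evaluation of sample size counts a negative rapid test among the reasons for withdrawal at screening. Study design sends negative children for PCR for other viruses and sets no positive result as an entry condition. If negatives are withdrawn, the covariate is constant in the analysed set. The two sections must be reconciled before it is used.

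**Conclusion.** The point holds as lost efficiency of unknown size. The unadjusted comparison is a valid analysis of a randomised trial, and nothing here shows bias, an inflated type I error or a shortfall against the stated power.

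The gain from prespecified adjustment runs from under one percentage point (R² up to 2%) through 2 points (5%) and 4 points (10%) to about 12 points (30%), starting from 80.1%. It rests on a difference of 0.5 day, an SD of 2, 254 analysed per arm, a comparison of means and an assumed R². The arithmetic is firm, but the documents do not show where in that range the trial lies. The change is recommended because it costs almost nothing and could help appreciably, not because the plan fails without it.

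**What to change.** In the Statistical criteria section, name the primary analysis: ANCOVA (PROC GLM) of illness duration on treatment, with Visit 1 total symptom score, Visit 1 temperature, age and country as covariates. Fix the list and the coding before unblinding.

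- Add the rapid-test result only if children with positive and with negative results are both analysed, and only after Study design and Evaluation of sample size have been reconciled on this.
- Use the same model at the interim and the final look, so that the O'Brien-Fleming bounds apply to one consistently defined statistic.
- Keep the unadjusted comparison as a sensitivity analysis, by Student's test and by Mann-Whitney, so that the normality check no longer decides which analysis is primary.

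The sample size can stay at 254 per arm, because no reduction should be taken on an R² that the documents do not support. The cost is SAP wording only: the data are already scheduled for collection and the SAS procedure is already listed.
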